Stroke is a leading cause of disability in adults in the US. Currently, IV tPA is the only FDA-approved acute therapy for treatment of ischemic stroke, and is routinely administered to patients in the ED within 4.5 hours of onset of stroke symptoms. After tPA administration in the ED, the patients are routinely monitored in the neurocritical care unit (NCCU) for at least 24 hours for frequent neurological exams and vital sign checks before being eligible to be transferred to a floor bed. While this practice is the current standard of care, there is no rigorous scientific evidence to suggest that all patients require intensive monitoring in the NCCU. In addition, ICU care is costly and ICU resources are scarce. We have recently analyzed the critical care needs and interventions of 153 patients who received IV tPA for acute ischemic stroke at JHH and JHBMC between 2010 and 2013. We found that over 80% of post-tPA patients did not have critical care needs (Faigle et al,

JHMIRB eFormA 01 Version 1 Dated: 11/18/13 manuscript submitted). Furthermore, our data show that 93% of patients without critical care needs by the end of the tPA infusion continue to have an uneventful hospital course with no further critical care needs. The risk of critical care needs for patients presenting with minor stroke symptoms, defined as a presenting NIHSS of 9 or less, was less than 1% if no ICU indication was present by the end of the tPA infusion. We hypothesize that patients who receive IV tPA for acute ischemic stroke in the ED may be safely monitored in a non-ICU environment if they do not have an ICU indication by the end of the tPA infusion and if their presenting NIHSS is below 10.

4. Study Procedures

Design:

The study is a multi-center (2 clinical sites) single arm, open label, pilot clinical trial. The aim is to provide proof-of-concept testing for the safety of non-ICU care in post-tPA patients in acute stroke. The null hypothesis (Ho) is that patients who are monitored in a non-ICU environment post-tPA administration will have ICU needs exceeding 6% of all patients. Six percent was chosen as a cut-off because this is the expected rate of hemorrhage after tPA administration in all stroke patients based on published literature.

The alternative hypothesis (Ha) is that no more than 6% of patients who are monitored in a non-ICU environment post-tPA administration will develop ICU needs.

Treatment Regimen:

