JHMIRB eFormA 01 Version 1 Dated: 11/18/13

Exclusion criteria:

For patients receiving IV tPA according to the current standard of care, the following exclusion criteria apply:

- Age <17 or >80
- ICU need or indication by the end of the tPA infusion
- NIHSS >9 at presentation or at the end of the tPA infusion
- Indication/need for endovascular recanalization therapy

6. Drugs/ Substances/ Devices

No experimental drug will be used in this trial. All patients will receive IV tPA per the standard of care. Tissue plasminogen activator (tPA) is FDA-approved for treatment of acute ischemic stroke, and will be administered at the standard dose for treatment of acute stroke: 0.9mg/kg, 10% IV bolus, and the rest by IV continuous infusion over one hour. Maximum dose is 90mg. tPA Indication and mode of IV tPA administration will occur according to the current standard of care.

7. Study Statistics

Baseline Demographics:

The sample size will be 50 patients, to assess the safety of non-ICU monitoring in post-tPA patients selected according to above criteria. The number of patients receiving IV tPA for acute ischemic stroke at Johns Hopkins Hospital and Johns Hopkins Bayview Medical Center is approximately 75 per year, fairly evenly divided between the 2 locations. Based on our retrospective analysis of 153 patients over 3 years between 2010 and 2012, 85 of 153 patients would have been eligible to participate in this study based on above inclusion and exclusion criteria. Assuming a constant rate of tPA administration per year, this would yield about 27 study subjects per year at JHH and JHBMC, assuming a rate of agreement of 65%. Based on this assessment, this study can be completed in less than two years.

Safety analysis:

Because this study is designed to assess safety, the safety analysis is the same as the primary outcome analysis, which is the assessment of the rate of ICU needs and need for ICU transfer developing in the first 24 hours after IV tPA administration. A DSMB (composed of one member independent of the investigator team) will conduct an analysis of the rate of ICU transfer in the study subjects.

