Need for ICU transfer (events) for patients monitored in the non-ICU setting will be evaluated after each subject completes 24 hours of post-tPA monitoring. During the phase of the study in which there are 1-9 subjects, the study will stop at any point there are two events in this group. During the phase of the study in which there are 10-20 subjects, the study will stop at any point if there are three events. During the phase of the study in which there are 20-40 subjects, the study will stop at any point if there are four events. During the phase of the study in which there are 40-50 subjects, the study will stop at any point if there are five events.

Primary endpoint:

 Need for ICU care/interventions (including intracerebral hemorrhage or cerebral edema with mass effect) within the first 24 hours after IV tPA administration will be the primary outcome measure.

Secondary endpoints:

- NIHSS at 24 hours
- NIHSS at discharge
- Modified Rankin Scale at discharge
- NIHSS at 90 days
- Modified Rankin Scale at 90 days
- Mortality at 90 days

Analysis for the secondary endpoints will be done comparing outcomes of study subjects with matched (age, race, NIHSS) controls from our de-identified stroke database of patients receiving IV tPA for acute ischemic stroke under the standard protocol.

Subject discontinuation:

Subjects have a right to withdraw from the study at any time. Subjects that decide to withdraw from the study within the first 24 hours will receive standard of care at the time of withdrawal. No data will be collected on the patient after voluntary withdrawal from the study.

The subject may be withdrawn from the study for any reasons: if it is in the best interest of the subject, intercurrent illness, adverse events, or worsening condition. The IRB, NINDS, the OHRP, the FDA, or other government agencies as part of their duties to ensure that research subjects are protected, may request the withdrawal of a subject because of protocol violations, administrative reasons, or any other valid and ethical reasons.

8. Risks

Risks potentially associated with non-ICU monitoring may result from delayed recognition of medical or neurological deterioration, with limited capability of rapid intervention in a non-ICU setting.

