Most complications related to IV tPA administration are neurological deterioration secondary to intracerebral hemorrhage. In our retrospective analysis, almost all patients who developed ICU needs after IV tPA developed such needs during the tPA infusion. In the present study, subjects are being monitored in the ED with frequent neurological examinations and vital sign checks during the tPA infusion, and for up to an additional hour, as it is the current standard of care. In the non-ICU setting, a stroke trained nurse will assess the patient upon admission to the floor, and then again after 1 hour, thereby ensuring adequate frequency of examinations and vital sign checks in the most critical post-tPA period. Thereafter, neurological exams and vital sign checks will be less frequent, every 2 hours for 8 hours, and then every 4 hours until 24 hours post-tPA are complete. Nurses will have special training in caring for post tPA patients, and will be familiar with risks and warning signs of tPA related hemorrhage and other complications. Per protocol, any change in neurological exam will result in a formal evaluation by the covering neurology resident or member of the inpatient team who will obtain an NIHSS. At JHH an RRT (with evaluation by the on-call NCCU fellow) for potential transfer to the NCCU will be activated for any increase in NIHSS > 3 points from baseline (post-tPA NIHSS). Similarly, any medical deterioration requiring ICU care in the judgment of the provider will result in activation of an RRT with potential transfer to the NCCU. Similarly, at JHBMC RRT activation for subjects will follow the same criteria, and includes discussion with the neurology Chief resident and NCCU fellow for potential transfer to the NCCU if deemed indicated.

Safety assessments will consist of monitoring and reporting adverse events (AE) and serious adverse events (SAE) that are considered to be related to non-ICU monitoring, all events of death, and any study specific issue of concern.

JHMIRB eFormA 01 Version 1 Dated: 11/18/13 An AE is defined as any unfavorable and unintended sign, symptom, or disease temporally associated with non-ICU monitoring.

This includes the following:

- Any event or change in condition within the first 24 hours after tPA administration that requires ICU care or ICU intervention.

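### Do the shared counts at 20 and 40 subjects, and the unstated counting base, leave the stopping rule undefined?

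*Combined protocol and SAP*

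**What the plan says.** Section 7 (Safety analysis) states that ICU-transfer events "will be evaluated after each subject completes 24 hours of post-tPA monitoring", so there is a look after every subject. Four sentences then set the boundary:

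- 1-9 subjects: "the study will stop at any point there are two events in this group".
- 10-20 subjects: "During the phase of the study in which there are 10-20 subjects, the study will stop at any point if there are three events".
- 20-40 subjects: "During the phase of the study in which there are 20-40 subjects, the study will stop at any point if there are four events".
- 40-50 subjects: "During the phase of the study in which there are 40-50 subjects, the study will stop at any point if there are five events".

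The same section has a one-member DSMB that "will conduct an analysis of the rate of ICU transfer in the study subjects". Section 4 (Design) places the boundary between the null and alternative hypotheses at an ICU-need rate of 6%. Section 3 reports that, for presenting NIHSS of 9 or less, the risk "was less than 1% if no ICU indication was present by the end of the tPA infusion". The documents give no stopping probabilities for the rule, so there is no stated figure to reproduce.

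**The concern.** The first boundary is clean (9, then 10), but the next two share an endpoint. Because a look follows every subject, one look falls exactly on 20 and another exactly on 40. If the third event occurs in subject 20, one sentence is met and its neighbour is not; the same is true if the fourth event occurs in subject 40. With no tie-break, the threshold might be chosen after the data are known, and that choice would decide whether the study ends or keeps enrolling.

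The counting base is the second worry. Only the first phase says what is counted, namely events in that group. The other three sentences say only that there are three, four or five events. If someone restarted the count in each phase, the rule would be much weaker. This is the only numerical stopping rule at study level; the NIHSS trigger in sections 4 and 8 acts on the individual patient.

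**Working it through.** **1. What the text does at the shared counts.** With three events at subject 20, the 10-20 sentence applies and is met, so the study stops. The 20-40 sentence also applies and is not met, but it contains no instruction to continue, so it does not cancel the stop. The same holds with four events at subject 40. Read literally, the lower threshold governs at both counts.

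**2. How often a shared count would be in dispute.** Assume cumulative counting, independent subjects and a constant event rate *p*, with *q* = 1 − *p*.

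*Look at 20.* This needs exactly two events in the first 19 subjects, not both in the first 9 (that would have stopped the study), and then an event in subject 20:

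[C(19,2) − C(9,2)] · p³ · q¹⁷ = (171 − 36) · p³ · q¹⁷ = 135 · p³ · q¹⁷

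- p = 6%: 135 × 0.000216 × 0.3493 = 0.0102, or 1.02%.
- p = 1%: 135 × 0.000001 × 0.8429 = 0.000114, or 0.011%.

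*Look at 40.* This needs exactly three events in the first 39 subjects without an earlier stop, and then an event in subject 40. There are C(39,3) = 9,139 placements of three events. Remove those with two or more in the first 9: C(9,2) × 30 + C(9,3) = 1,080 + 84 = 1,164. Then remove the other placements with all three in the first 20 (lower threshold at 20): C(20,3) − [C(9,2) × 11 + C(9,3)] = 1,140 − 480 = 660. This leaves 7,315. With the higher threshold at 20, the last removal is C(19,3) − [C(9,2) × 10 + C(9,3)] = 969 − 444 = 525, which leaves 7,450.

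- p = 6%: 7,315 × 0.06⁴ × 0.94³⁶ = 7,315 × 0.00001296 × 0.1078 = 0.0102, or 1.02% (1.04% with 7,450).
- p = 1%: 7,315 × 0.01⁴ × 0.6964 = 0.000051, or 0.005%.

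The chance of any disputed look is therefore about 2.0-2.1% at 6% and about 0.02% at 1%.

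**3. What the tie-break changes overall.** An exact recursion over subjects 1 to 50, stopping when the cumulative count reaches the threshold in force, gives:

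| True rate | Lower threshold at 20 and 40 | Higher threshold at 20 and 40 | Difference (points) |
|---|---|---|---|
| 1% | 0.446% | 0.432% | 0.01 |
| 2% | 2.26% | 2.16% | 0.1 |
| 6% | 29.6% | 28.8% | 0.8 |
| 10% | 67.4% | 66.7% | 0.8 (before rounding) |

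The two mixed tie-breaks fall in between (29.1% and 29.4% at 6%). Expected enrolment at 6% is 41.9 subjects under the lower thresholds and 42.1 under the higher. A simulation of 400,000 trials at 6% with the lower thresholds also gives 29.6%. The difference is smaller than the chance of a disputed look because many studies that continued past one would stop later anyway.

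**4. The counting base.** Suppose the count restarted in each phase, with blocks of 9, 11, 20 and 10 subjects. At 6% the chance of passing all four blocks is about 0.9022 × 0.9753 × 0.9710 × 0.9998 = 0.854, so stopping falls to about 14.6% (14.1-14.6% across tie-breaks), half the cumulative figure. This reading does not fit the text:

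- Each phase is defined by how many subjects are in the study, which is a running total, and the events are stated in the same running form.
- In the first phase, that group is everyone enrolled so far, so counting in the group and counting cumulatively are the same thing.
- The DSMB looks at the rate among the study subjects, not within a phase.
- Under restart, the last phase would need five events in about 10 subjects, and 1 + 2 + 3 + 4 = 10 of 50 (20%) could occur without a stop, against a 6% cut-off. Cumulatively the most is 4 of 50 (8%).

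Thresholds that rise by one as the sample grows are the shape of a cumulative boundary.

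**The case for a change.** The best case for a change is that a safety boundary should not depend on inference. At 3/20, a DSMB member could say in good faith that the study has entered the four-event phase. The phrase about the group appears in the first sentence and then disappears, so a per-phase reading is not excluded by any explicit word. Stopping rules exist for the case where the expected rate of under 1% turns out wrong. One or two sentences would close both gaps at almost no cost.

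Of this, the textual facts stand: the ranges do overlap, and no word such as cumulative or total appears. The argument from consequences is weak. Taking the looser threshold at 20 or 40 means setting aside a stop condition that has been met, and even then the effect is under one percentage point. The large contrast, about 14% against 29%, arises only under a restart reading that the rule's structure argues against. A tidier sentence would record what a sensible reader already does; it would not alter any decision.

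**Conclusion.** The concern does not hold as a reason to change the plan. The shared endpoints are a clerical slip, and the missing counting base is a gap that analysts and the DSMB would fill in the obvious way. Followed literally, the rule stops the study at three events by subject 20 and at four by subject 40. Resolving both ties the other way lowers overall stopping by 0.8 points at a true 6% and by about 0.01 points at 1%, and adds about 0.2 subjects to expected enrolment at 6%.

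These figures assume cumulative counting, a look after every subject, independent subjects and a constant event rate. The 1%, 2% and 10% rates are illustrative; the documents give only under 1% and 6%. The conclusion would be different only if the study team meant the count to restart in each phase, and nothing in the protocol suggests that.

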Criteria for RRT activation for potential ICU transfer are at the discretion of the treating medical team. In addition to commonly accepted criteria for ICU transfer, worsening of the neurological exam of >3 points on the NIHSS will trigger a STAT head CT and transfer to ICU for intense monitoring if the CT reveals intracerebral hemorrhage or increasing cerebral edema with signs of mass effect. This is based on previously established criteria in the ECASS trial, in which neurologic worsening with an NIHSS >3 was used to evaluate for potential symptomatic intracranial hemorrhage ¹.

Other commonly accepted criteria for need for ICU transfer may include, but may not be limited to, the following:

- uncontrolled hypertension requiring active titration of IV antihypertensives (more than two doses within 30 minutes or frequent dosing (e.g., q 1hr x 3 doses))
- need for vasopressors either for symptomatic systemic hypotension or blood pressure augmentation
- need for invasive hemodynamic monitoring
- uncontrolled hyperglycemia requiring IV Insulin
- respiratory compromise resulting in either initiation of bilevel positive airway pressure (BiPAP) or mechanical ventilation
- arterial bleeding
- management of cerebral edema and increased ICP
- need for neurosurgical intervention such as decompressive craniectomy
- interventional angiography with or without intervention

Once the decision is made to move the patient to the NCCU, subjects will receive routine NCCU care and the subject will be adjudicated as meeting the primary outcome.

After 24 hours (+/- 4 hours) patients will receive either a head CT without contrast or an MRI brain as it is the current standard of care, and will receive an NIHSS by a member of the study team. Thereafter, patients will continue to receive standard care for stroke patients, and will be discharged from the hospital, when medically stable, to the appropriate rehabilitation setting, if any. At the time of discharge all patients will receive a modified Rankin score, and NIHSS.

All patients will return for a follow-up visit at 90 days and will receive a modified Rankin score, and NIHSS. This will be the secondary outcome.

The subject's involvement with this study will end at 90 days after the assessment.

5. Inclusion/Exclusion Criteria

Subject selection:

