- AEs not previously observed in the subject that emerge during the protocol-specified AE reporting period, including signs or symptoms associated with ischemic stroke that were not present prior to the AE reporting period.
- Complications that occur as a result of protocol-mandated interventions (e.g., invasive procedures such as cardiac catheterizations).
- Preexisting medical conditions (other than the condition being studied) judged by the investigator to have worsened in severity or frequency or changed in character during the protocol-specified AE reporting period.

An AE should be classified as an SAE if:

- It results in death
- It is life threatening
- It requires prolonged hospitalization
- It results in persistent or significant disability/incapacity

All AEs and SAEs whether volunteered by the subject, discovered by study personnel during questioning, or detected through physical examination, laboratory test, or other means will be reported appropriately.

9. Benefits

By potentially avoiding an unnecessary ICU stay, participants may benefit from an expedited stroke work-up and reduced length of hospital stay. Admission directly to the floor would result in less frequent interruptions for neurological exams and vital sign checks, which may improve quality of sleep. In addition, bypassing ICU care would reduce the number of hand-offs between different providers and provider teams, and thereby reduce the chance for medical errors. Avoiding unnecessary ICU admission would greatly reduce cost for stroke admissions and reduce the financial burden on society associated with acute stroke care.

10. Payment and Remuneration

There will be no payment to participants.

11. Costs

There are no anticipated additional costs to participants.

12. References

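### The SAE list covers prolonged hospitalization but not a new admission, and the AE reporting period is never stated, so some readmissions before day 90 would not be graded serious

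*Combined protocol and SAP*

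**What the plan says.** **Seriousness (Section 8, Risks).** An AE is serious if it meets one of four criteria: "It results in death"; "It is life threatening"; "It requires prolonged hospitalization"; "It results in persistent or significant disability/incapacity". A new inpatient admission is not among them.

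**What counts as an AE (Section 8).** An AE is "any unfavorable and unintended sign, symptom, or disease temporally associated with non-ICU monitoring". One of the listed types is new events that "emerge during the protocol-specified AE reporting period"; worsened pre-existing conditions are tied to the same period. Just before the definition, the scope of safety reporting is limited to AEs and SAEs considered related to non-ICU monitoring, all deaths, and any study-specific concern.

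**Follow-up (Section 4, Study Procedures).** The non-ICU monitoring schedule ends 24 hours after tPA. Subjects return at 90 days for a modified Rankin score and NIHSS, and: "The subject's involvement with this study will end at 90 days after the assessment".

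**Length of stay (Section 9, Benefits).** By avoiding an unnecessary ICU stay, "participants may benefit from an expedited stroke work-up and reduced length of hospital stay".

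**The concern.** The first objective is to establish that non-ICU monitoring after tPA is safe, and a shorter stay is named as a possible benefit. A reader of the results will want to know whether subjects came back to hospital after discharge. Seriousness criteria would be expected to pick that up, but here the hospital criterion refers only to prolongation. The period over which events are to be reported is also left open, so the two sites could apply different windows and each believe it was following the protocol. At stake is the completeness of the late safety record, not the primary result.

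**Working it through.** No arithmetic applies. The check sets the relevant provisions side by side.

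**1. Does any SAE criterion cover a readmission?** Take a subject discharged home and readmitted on, say, day 10 for a short stay, with an event that is not fatal, not life threatening and leaves no lasting disability.

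| Section 8 criterion | Met? |
|---|---|
| Death | No |
| Life threatening | No |
| Prolonged hospitalization | No for a short stay; arguable for a long one |
| Persistent or significant disability | No |

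The event is not serious under the list. Relatedness does not alter this: it decides whether an event is reported, not how it is graded.

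**2. Is the event inside the reporting period?** The AE reporting period is mentioned three times, all within two bullets of Section 8, and its start and end are given nowhere. Two time frames could be taken for it:

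- *24 hours.* The AE definition is tied to non-ICU monitoring, and the Section 4 schedule stops at 24 hours. The ICU-need bullet in Section 8 uses the same window. On this reading the day-10 readmission may not be an AE at all.
- *90 days.* Section 4 ends the subject's involvement at 90 days. On this reading the readmission can be an AE, but by step 1 it is still not serious.

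Neither time frame is called the AE reporting period.

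**3. Would anything else record it?**

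- Primary endpoint (Section 7): ICU need within 24 hours. No.
- Stopping rule (Section 7): counts ICU-transfer events, evaluated as each subject completes 24 hours. No.
- DSMB (Section 7): its stated task is the rate of ICU transfer. No.
- Secondary endpoints (Section 7): NIHSS, modified Rankin score and 90-day mortality. These reflect death or a deficit still present when measured, not a readmission from which the subject recovered.
- Visits (Section 4): no contact is scheduled between discharge and day 90, and the 90-day visit lists no question about readmission.

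**4. Would changing the SAE list be enough?** No. With the scope sentence and the AE definition in Section 8 left as they are, a readmission judged unrelated, or too late to be temporally associated with monitoring, would still fall outside reporting.

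**The case against.** The strongest reply is that this is a matter of grading, not of lost data. Section 8 covers AEs as well as SAEs and says that both will be reported, so a related readmission within the period would still appear as an AE. Many of the late events one would worry about, such as a delayed bleed or a recurrent stroke, would meet the life-threatening or disability criterion. All deaths are reported, and the 90-day assessments pick up lasting deficit. The hospitalization wording might also stretch to a long new stay. All of this stands, and it narrows the gap to a non-fatal, non-life-threatening, non-disabling and short readmission. It does not close the gap, because such an event is not serious under the list and its status as an AE depends on a period that is not stated.

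A reader might infer more than the documents allow:

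- *That readmission is the main late harm of this pathway.* Section 8 names a different risk: delayed recognition of deterioration, with limited capacity to intervene quickly outside the ICU. Early discharge is not an intervention; after 24 hours subjects receive standard care and leave when medically stable.
- *That the protocol promises a shorter stay.* Section 9 offers it only as something that may happen.
- *That unreported readmissions could rival the two to five events that stop the study.* No readmission rate is given. Those thresholds count ICU needs in the first 24 hours, not admissions over 90 days, and some readmissions would be serious under the existing criteria. The comparison is not like with like.

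**Conclusion.** The point holds as a minor, inexpensive improvement to safety reporting. Followed exactly, the SAE list leaves ungraded as serious a readmission that is not fatal, life threatening, disabling or prolonged, even when it is judged related, and no endpoint or stopping rule would capture it. The AE reporting period is referred to but never given; on its own that would be missing detail, but here it also leaves open whether such a readmission counts as an AE.

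The size cannot be put in numbers: the documents give no readmission rate and the argument needs none. The conclusion rests on reading the four criteria as a complete list and prolonged hospitalization in its ordinary sense, which a short new stay does not meet. It does not show that the trial would reach a wrong conclusion on its primary question. The primary endpoint, stopping rule and sample size are unaffected.

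**What to change.** Four changes, which work only together:

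1. **SAE criterion (Section 8).** Replace the hospitalization item with: *requires inpatient hospitalization (including readmission) or prolongs existing hospitalization*.
2. **Reporting period (Section 8).** State that SAEs are collected from consent to the 90-day assessment, and give the period for non-serious AEs a start and an end as well.
3. **90-day visit (Section 4).** Add a question on any readmission since discharge, with its date and cause.
4. **Scope sentence and AE definition (Section 8).** Amend the limit to events considered related to non-ICU monitoring, and the limit to events temporally associated with it, so that readmissions to day 90 are recorded whatever their judged relatedness. Record relatedness as a separate item.

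The cost is a few sentences of protocol text and one question at a visit that already takes place. The downside is a few more SAE reports, most of them probably unrelated to the monitoring setting.
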